Study Protocol

Official Title: Zoledronic Acid for Osteoporotic Fracture Prevention (ZEST II)

ClinicalTrials.gov ID (NCT number): NCT02589600

Protocol Date: 3/30/2023

Scientific Background

Impact of Osteoporosis and Fractures in Long-Term Care Residents:

Osteoporosis is devastating, particularly for the elderly. Each year 250,000 Americans suffer a hip fracture, of whom 20% die in the subsequent year, 25% are institutionalized, and ≤50% fully recover. Because the fastest-growing segment of the U.S. population is women >85 years, and 1/3 of those who fracture are over age 90, the number of patients with hip fractures will double in the next 15 years (1,2) and the current annual cost of \$17 billion will double by 2040 (3).

Osteoporosis' impact for America's 2 million long-term care (LTC) residents is even more dramatic, with a prevalence of 85% (4) and an 11% annual incidence of nonvertebral fractures. Such residents were hospitalized ≥15 times as often as those without fracture (5) and those with hip or vertebral fractures are at 2-3x greater risk for future fracture (6,7). A vertebral fracture is associated with back pain (8-11), decreased mobility, increased bed rest (12), and higher rates of hospitalization and mortality (13,14). A recent review of 60,000 nursing home patients reported that following a hip fracture, 36% died and 53% died or developed new total dependence in 6 months (15).

Osteoporosis Therapy in the Elderly:

Osteoporosis Therapy is Safe and Efficacious in Healthy Elderly: The PI reported on the first prospective, randomized, placebo-controlled, multi-center trial of daily bisphosphonate therapy in healthy LTC residents (16). At 2 years, spine and femoral neck bone density had increased by 4.4% and 3.2%, respectively, with the bisphosphonate alendronate. This study demonstrated that daily alendronate was safe, well-tolerated, and improved bone mass in independent, ambulatory, cognitively intact women, able to take a daily oral bisphosphonate by themselves. The study excluded women with multiple medical problems, limited mobility, cancers, cognitive impairment, or diseases that impact bone and did not address the question if such therapy was safe or efficacious in institutionalized elderly.

Post-hoc pivotal trial subgroup analyses comparing those >75 to those <75 years suggest zoledronic acid (17), teriparatide (18) and denosumab (19) are efficacious in older very healthy women who qualify for a clinical trial. These trials only included women who were healthy, cognitively intact, fully ambulatory, and able to sign their own consent. Fracture reduction data in frail elderly are lacking.

Osteoporosis Therapy in Frail Elderly may not be Clinically Effective:

There are little data on frail elderly or non-healthy LTC residents (20,21). In addition, the limited available data questions the efficacy of bisphosphonate in frail elderly. For example, in the HIP study, fracture reduction was not demonstrated with an oral bisphosphonate in women over age 80 enrolled based on clinical risk factors only (22). Furthermore, the PI's ZEST study in frail LTC residents, demonstrated improvement of BMD at the hip and spine with zoledronic acid, however no fracture reduction trend was observed. The majority of these patients were cognitively impaired, sedentary and had multiple comorbid conditions, excluding them from an industry trial. Fracture reduction data are lacking in these vulnerable patients. The March 2011 NIH/ASBMR Forum on Aging and Skeletal Health echoed the critical need for osteoporosis research, a fracture reduction study and treatment for frail LTC residents (23).

Why would therapy fail in frail elderly? Both skeletal and nonskeletal factors in frail elderly may mask a fracture reduction benefit from a potent bisphosphonate. Despite the improvement in bone density and reduction in bone turnover (both independent contributors to fracture reduction), frail individuals may not benefit due to severely compromised skeletal integrity from poor trabecular connectivity (disconnected rods and plates), increased trabecular fragments,

Study Design & Methods

This is a 3-year, randomized, double-blind, calcium and vitamin D controlled trial with the antiresorptive agent zoledronic acid (Reclast).

The study consists of 5 main visits (Screening, Randomization, Month 12, Month 24, and Month 36), with pre and post infusion safety check visits. Pre-infusion safety check visits will be done up to 2 weeks prior to receiving the annual IV study drug or placebo. Post-infusion safety check visits will be done 1-3 days after infusion.

We have chosen yearly intravenous zoledronic acid because it has been shown to significantly reduce vertebral fractures by 70%, all clinical fractures by 35%, hip fractures by 41% in the pivotal trial that included older healthy women. Additionally, in a sub-analysis including women \geq 75 years old, yearly zoledronic acid decreased vertebral fractures by 66% over 3 years. Moreover, fracture reduction after 2 and 3 infusions were 47% and 39%, respectively. Because nursing home patients are difficult to treat and resources are limited, the intravenous injection has several advantages. It does not require fasting, administration at a specific time of day, or sitting up, which are all significant practical advantages over a weekly oral bisphosphonate. All patients without liver abnormalities will be offered acetaminophen prior to the infusion and for 2 days post-infusion to decrease acute phase reactions and maintain the blind.

Rationale for yearly dose versus single dose: Despite the improvement in density over 2 years after a single dose in our initial ZEST study, we will follow conventional yearly dosing that demonstrated fracture reduction in the pivotal trials. In the event we do not find a fracture reduction benefit, we wanted to be certain that it would not be due to under-dosing.

At the request of the DSMB, we will be offering a Follow-up Extension phase to this study to continue data collection on the skeletal health of participants in the ZEST II study. Therapy and blood work will not be provided throughout the follow-up extension. There will be a maximum of three visits in the follow-up extension. The number of visits that a participant will have can be determined by when they have completed their Month 36 visit. Participants who have completed the Month 36 visit on or before July 31, 2019 will have three follow-up visits. Participants who have completed the Month 36 visit on or before July 31, 2020 will have two follow-up visits. Participants who have completed the Month 36 visit on or before July 31, 2021 will have one follow-up visit. Participants who do not complete the Month 36 visit before August 1, 2021 will not be eligible to participate in the follow-up extension.

SKELETAL ASSESSMENTS

Fragility Fractures: From baseline to the end of follow-up, nonvertebral and clinical vertebral fractures will be identified by the electronic medical record alert and by Theradoc (a real-time, stand-alone clinical alert and decision support application used at UPMC LTC facilities, with custom rules to be written for this study to provide detection and identification of participants presenting to any UPMC facility so that generated alerts will be sent to the study team via e-mail). In addition, participants/charts will be queried at approx. 6 month intervals for clinical fragility fractures defined as a fracture following a fall from a standing or sitting height. All reported fractures will be verified by obtaining the radiology report confirming the fractures. We exclude fingers, toes, face, and skull fractures. All femur fractures will be examined for atypical fractures using ASBMR criteria (128).

Vertebral Fractures: We will use the presence of thoracic or lumbar vertebral fractures as determined by Vertebral Fracture Assessment (VFA is DXA-derived) as the primary classification of vertebral fracture performed annually (53, 73, 129). The fractures will be scored according to the method of Genant (130, 131) and considered a grade 1 mild vertebral deformity, a grade 2 moderate vertebral deformity, or a grade 3 severe vertebral deformity. We will assess vertebral fractures at baseline, 12, 24, and 36 months, as well as at follow-up visits 1, 2, and 3. Conventional x-rays or a MRI that demonstrates a fracture will also be used.

Indices of Bone Mineral Metabolism: Serum will be assayed for 25-hydroxyvitamin D2/D3 for the secondary aim. We will collect serum for bone turnover markers at baseline and M36 for responder analysis for the exploratory aim (60, 65-67, 132, 133). To assess bone resorption, we will measure serum CTX. We will assess bone formation with P1NP. Serum will be archived for future analyses.

Trabecular Bone Score (TBS): TBS, a new gray-level texture measurement is evaluated in the same region of interest as the spine BMD using the iNsight Software version 1.9 (54-58). TBS utilizes the 2-D DXA spine images and provides 3-D microarchitectural images and parameters (57, 59). The precision for TBS ranged from 1.1 to 1.9% (55). In previous studies, TBS was independent of BMD for fracture prediction and significantly improved risk protection (80, 81). TBS is only minimally affected by sclerosis/osteoarthritis (57). For the exploratory aim, we will examine TBS from DXA images.

Eligibility Criteria

Inclusion Criteria:

Our goal is to include older women with osteoporosis or low bone mass (with fracture risk) unless there is a known contraindication to therapy. We will enroll ambulatory women age ≥ 65 years including those using assistive devices to maximize generalizability, if they:

- 1) Reside in long-term care (LTC) including Managed Senior Communities which provide the following: (a) An environment engineered to prevent falls (handrails, ramps) and are ADA accessible; (b) Facilitate access to medical attention (pull cords, life-alerts, or other electronic means); (c) ADA accessible transportation services available; (d) Provide or coordinate meals; (e) Secure building (automatically locked door or buzzer system, security cameras).
- 2) Have a) osteoporosis by axial bone density (spine, hip or forearm BMD T-score ≤ -2.5 SD)(99,100); or b) a previous adult fragility fracture of the spine or hip; or, c) would be treated based on FRAX (101,102) NOF treatment thresholds of a 10 year risk of $\geq 20\%$ for a major osteoporotic fracture or $\geq 3\%$ for hip fracture using femoral neck BMD (103).

Follow-up Extension Inclusion Criteria:

- 1) Complete Month 36 Visit on or before July 31, 2021.

Exclusion Criteria:

We will exclude:

- 1) Men because osteoporosis is less common in men and our initial ZEST 1 study only included women.
- 2) Institutionalized women with subacute illnesses surviving or discharged in < 3 years.
- 3) Women currently on bisphosphonate, denosumab, or teriparatide therapy or who have been on a bisphosphonate for greater than 1 year during the previous 2 years because bisphosphonates are long acting (104).
- 4) Patients with a calculated creatinine clearance < 35 ml/min (105,106) or who have a contraindication for bisphosphonates (allergy, hypocalcemia).
- 5) Women scheduled for a tooth extraction to avoid jaw osteonecrosis (107-109).

We will screen with a detailed history, chart review, and baseline laboratory analyses. Women with vitamin D levels <25 ng/mL (110,111) will be treated with vitamin D 50,000 IU/wk for 8 weeks (112,113). The patient will be enrolled if the follow-up vitamin D level is \geq 25 ng/mL. Vitamin D levels <25 ng/mL are associated with falls (114,115) and our prior ZEST 1 Study data supports a level \geq 25 ng/mL for better performance and improved walking (98). Patients can continue on glucocorticoids and anticonvulsants because their use is common (116). Women on raloxifene, calcitonin or using protective hip pads will be allowed to participate.

Exclusion Criteria #3, #4, and #5 will not apply to participants in the Follow-up Extension phase of this study.

Statistical Considerations

Overview: All statistical analyses will use SAS® version 9 (SAS Institute, Inc., Cary, North Carolina) based on intention-to-treat. First, appropriate descriptive statistics will be computed and graphical summarizations made for all variables for each treatment group for each time point as well as raw and percent change scores from baseline to obtain an overall sense of the distributional characteristics, missing values and general data quality. Second, baseline measures will be compared across arms using independent samples t- and a Wilcoxon rank sum tests, as appropriate, for continuous variables and chi-square and Fisher's exact tests, as appropriate, for categorical variables. Although no significant differences are expected due to randomization and large sample size, any variables found to be significantly different will be accounted for by including them as covariates in sensitivity analyses. Third, main analyses will be performed using a negative binomial regression model. Finally, exploratory analyses will be performed.

Main Analyses: First, we will fit a series of negative binomial regression implemented in the SAS® GENMOD procedure with each fracture outcome as the dependent variable; duration of follow-up as an offset to account for each participant's exposure; treatment arm as the main independent factor of interest; and any covariates deemed important as additional independent variables in sensitivity analyses. The incident rate ratio and its statistical significance at $\alpha=0.05$ level for the primary outcome of all new fractures will serve as a formal test of the main fracture reduction hypothesis (H1). Second, we will fit a series of linear mixed models using the SAS® MIXED procedure with raw and percent change each from baseline in each of the continuous outcomes representing laboratory measures related to safety as the dependent variable; treatment arm, follow-up time point (12-/24-/36-month, as available) and their interaction as the

fixed effects of interest; and a subject random effect. For some measures, we will fit simpler models (due to only one planned post-infusion assessment) using the GLM procedure with raw and percent change each as the dependent variable, and treatment arm as the main factor of interest. We will appropriately construct sets of contrasts to test various hypotheses of interest by comparing the said change over time between the two arms. Third, we will fit a series of logistic regression models using the SAS® LOGISTIC procedure with each incident dichotomous adverse event during the 36-month follow-up (any and specific types of adverse events) as the dependent variable, and treatment arm as the independent factor of interest. The resulting odds ratios and levels of significances will be used to test the specific hypotheses for Aim 2. We will repeat all main analysis after stratification by institutional setting (assisted living/nursing home).

Findings from the proposed trial will be most useful if (a) we can also identify a target sub-population of the long-term care that is most likely to benefit from zoledronic acid and/or least likely to experience side effects; and (b) we can speculate whether fracture reduction or non-reduction in women, despite improvement in BMD, depends on bone microstructure as measured by TBS. Therefore, using several techniques, some with an exploratory data mining philosophy, we will identify such sub-populations to address Aim 3(a). First, we will include all baseline clinical and laboratory characteristics, one-at-a-time, as an additional fixed effect in the models above, along with an interaction term with treatment group. Statistical significance of the interaction term will be interpreted as a patient baseline characteristic whose levels exhibit potentially differential treatment effects and/or safety profiles. Second, we will stratify analyses by such baseline criteria to actually obtain preliminary estimates of subgroup-specific treatment effects/safety differences. Third (data mining), using only the active arm, we will fit a series of logistic regression models using the SAS® LOGISTIC procedure and classification tree models using Salford Predictive Miner® software (Salford Systems, Inc., San Diego, California) with incident fracture as the dichotomous response variable; and baseline characteristics as predictors. Logistic models are more efficient when associations are linear, and hard-to-discover higher order interactions and non-linearity and/or multicollinearities among predictors do not exist, while classification tree models are more efficient when they do exist. Thus we will use both methods to obtain areas under the receiver operator characteristic curve (AUROCC) to quantify predictive accuracy, and use the results from the method with a greater AUROCC. For logistic regression we will use the backward elimination and for classification trees minimum misclassification-complexity cost tree to guard against overfitting. We will use the method of DeLong to obtain statistical significance of the differences in predictive accuracy between the models. For predicting improvements in continuous BMD change outcomes, we will employ a similar approach but with standard multiple linear regression and regression tree models and proportion of explained variance (R²) to quantify predictive accuracy.

For Aim 3(b), the association between zoledronic acid, BMD, TBS and fracture reduction will be explored in two ways. First, we proposed above to examine the effect of the study drug on TBS with standard linear models. Second, using only the active arm of the trial, we will fit a negative binomial model with number of fractures within 3 years as the dependent variable; and baseline BMD, 3-year change in BMD, baseline TBS, and 3-year change in TBS as independent variables. The statistical significance of regression coefficients for TBS measures will be interpreted as evidence supporting that fractures over a 3-year period depend on TBS and its changes over the same period independent of BMD.

Exploratory Analyses: We will perform exploratory analyses to assess the robustness of results and make more refined conclusions. For example, we will stratify adverse event and fracture

analyses to identify any differences between short- and long-term effects and/or within organ systems.

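### The laboratory change-from-baseline models do not list the baseline value, and covariates for the fracture sensitivity analysis are picked by baseline significance or left open

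*Protocol*

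**What the plan says.** **Laboratory models.** Under Statistical Considerations, Main Analyses, the Protocol fits mixed models "with raw and percent change each from baseline in each of the continuous outcomes representing laboratory measures related to safety as the dependent variable". The fixed effects it lists are arm, follow-up time point and their interaction, with a subject random effect. Measures with a single planned post-infusion assessment are analysed "using the GLM procedure with raw and percent change each as the dependent variable, and treatment arm as the main factor of interest". Neither list contains the baseline value of the measure.

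**Fracture model.** The primary model is a negative binomial regression with a follow-up offset and treatment arm. Covariates enter only in sensitivity analyses, by two routes:

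- The Overview, repeated in the SAP, tests baseline measures between arms and says that "any variables found to be significantly different will be accounted for by including them as covariates in sensitivity analyses". No significance level is given for these tests, and the variables to be tested are not listed.
- Main Analyses adds "any covariates deemed important as additional independent variables in sensitivity analyses". No variable, criterion or timing is given.

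**Other uses of baseline data.** For Aim 3(a) the Protocol enters "all baseline clinical and laboratory characteristics, one-at-a-time, as an additional fixed effect in the models above", each with a treatment interaction, to search for subgroups. The main analyses are also repeated by institutional setting. For Aim 3(b), in the active arm only, a fracture-count model uses "baseline BMD, 3-year change in BMD, baseline TBS, and 3-year change in TBS as independent variables".

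**The concern.** When the outcome is change from baseline, the baseline value is usually the strongest covariate available. Leaving it out gives a valid comparison on average, but a less precise one, and any chance difference at baseline carries into the estimate. These models serve the safety comparison, where precision is useful.

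In the fracture model, a significant baseline difference between randomized arms reflects chance. It says nothing about whether the variable predicts fracture, so the rule can bring in an irrelevant variable and pass over a strong predictor. The open clause could repair this, but as written it allows the set to be chosen after the data are seen. A sensitivity analysis built this way lends little support to the primary result and does little to challenge it.

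The Protocol itself points to better candidates. The Scientific Background puts future fracture risk at two to three times higher after a hip or vertebral fracture. Vertebral fractures are assessed at baseline. Aim 3(b) treats baseline BMD as a possible predictor of fracture count.

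**Working it through.** The two documents give no sample size, power, laboratory SD or correlation, so there is no planned figure to reproduce. The correlations below are assumptions, shown as a range.

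**1. Raw change at one visit.** Let rho be the correlation between baseline and follow-up, with both variances equal to 1.

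- Variance of the change score: 2(1 − rho).
- Residual variance once baseline is in the model: 1 − rho².
- Ratio: (1 − rho²) / [2(1 − rho)] = (1 + rho)/2.

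| rho | Change score | With baseline | Ratio |
|---|---|---|---|
| 0.5 | 1.0 | 0.75 | 0.75 |
| 0.7 | 0.6 | 0.51 | 0.85 |
| 0.9 | 0.2 | 0.19 | 0.95 |

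Read the other way, the model without baseline needs 2/(1 + rho) − 1 more patients for equal precision: 33%, 18% or 5%.

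**2. Mean of the three visits, equal correlations.** The change has variance (1 + 2rho)/3 + 1 − 2rho = 4(1 − rho)/3. With baseline the variance is (1 + 2rho)/3 − rho² = (1 − rho)(1 + 3rho)/3. The ratio is (1 + 3rho)/4 = 0.625, 0.775 or 0.925.

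**3. Narrowed baseline.** Equal variances may not hold. Enrolment requires vitamin D of at least 25 ng/mL and excludes creatinine clearance below 35 ml/min, which affects at least two of the listed measures (25-hydroxyvitamin D and eGFR). Suppose the baseline SD is cut to 80% with the slope unchanged, so that the baseline variance is 0.64. The change then has variance 0.64(1 − rho)² + (1 − rho²), and the ratio is (1 + rho) / [0.64(1 − rho) + (1 + rho)]:

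- rho 0.5: 1.5/1.82 = 0.82
- rho 0.7: 1.7/1.892 = 0.90
- rho 0.9: 1.9/1.964 = 0.97

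About a third of the gain goes.

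**4. Percent change.** The formulas above do not cover it. Simulation with a lognormal measure gives ratios of 0.75–0.78, 0.85–0.86 and 0.95 at coefficients of variation of 5–30%, and 0.82, 0.88 and 0.96 at 50%. The gain is similar or somewhat smaller.

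**5. Does Aim 3(a) already supply the baseline term?** No. It adds baseline variables singly, with a treatment interaction, to look for differential effects. The main laboratory contrasts are still read from models that do not list baseline.

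**6. The significance rule.** If the baseline tests use 0.05 (an assumption, since no level is stated), a strong predictor of fracture and an irrelevant variable each have a 5% chance of selection under randomization. With 20 independent tests, the chance of at least one selection is 1 − 0.95^20 = 64%, with 20 × 0.05 = 1 expected. The Overview itself expects no significant differences.

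**The case against.** The strongest reply is that nothing here is an error in the main result. That stands. The formal test of the fracture hypothesis uses the arm-only model with an offset, and no document ties a decision to the precision of the laboratory contrasts.

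The Protocol describes its laboratory terms as those of interest, which may name the tested terms without ruling out a baseline adjuster. That also stands: the documents show that baseline is not listed, not that it is excluded. If it is intended, writing it in costs one line.

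The open clause could admit prior fracture or BMD. It could; the fault is that nothing is fixed in advance. Aim 3(a) puts baseline clinical factors into the fracture model, and the repeats by setting use one of the candidates. Neither amounts to a single adjusted model, but both mean that baseline prognosis is not ignored altogether.

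Three stronger readings are tempting, and the documents do not support them.

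- **That the primary test is biased or its type I error inflated.** Neither covariate route touches it. Chance imbalance is already reflected in the unadjusted interval.
- **That the fracture test would gain power.** With a mean of 0.33 fractures (11% a year for 3 years), and assumed prior-fracture prevalence of 40%, dispersion of 0.3–1.0 and rate ratio of 0.65, adjusting for prior fracture cuts the variance of the log rate ratio by about 2.9% if prior fracture doubles risk, or 6.5–6.7% if it triples it. This counts only if the adjusted model carries the test, which is not proposed.
- **That most chance imbalance goes uncorrected in the sensitivity analysis.** Selection at p < 0.05 leaves 72% of the variance due to chance imbalance in a given covariate. That holds only if the baseline tests use 0.05 and the open clause adds nothing.

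**Conclusion.** The point holds as a low-cost improvement, not as an error in the main result.

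The firmer part is the laboratory models. Baseline is not listed, Aim 3(a) does not supply it as an adjustment, and adding it should give a modest gain. For raw change at one visit the variance ratio is about 0.75 to 0.95 over the assumed correlations with equal variances, or 0.82 to 0.97 if the baseline SD is cut to 80%. The actual correlations and spreads are not in the documents.

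The second part rests on the text rather than on arithmetic. Selection by between-arm significance is not selection by prognostic value, and the alternative route names nothing. The validity and power of the primary fracture test are unchanged. What improves is how much the sensitivity analysis can tell a reader.

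**What to change.** 1. Add the baseline value of the measure to every laboratory change model, raw and percent, and a baseline-by-visit term to the mixed models. No participant is lost, because anyone with a change score has a baseline value.
2. Drop baseline significance as a rule for selecting covariates, and replace the open clause with one named adjusted model: age, prior hip or vertebral fracture (history plus baseline VFA), baseline hip BMD and institutional setting. Fill missing baseline values by a simple rule pooled across arms. Fix the set blind to outcomes by arm.
3. Keep the unadjusted negative binomial model primary, and report the adjusted model as the named sensitivity analysis.

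A practical note on coding setting: eligibility admits women who "Reside in long-term care (LTC) including Managed Senior Communities which provide the following" certain services, whereas the stratified repeats name only assisted living and nursing home. The covariate needs a category for every setting admitted. How the stratified repeats should place these women is a separate question.

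The cost is SAP wording, one extra model per fracture outcome and simple baseline imputation, since the documents do not show that hip BMD is complete at baseline.

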## **Study Statistical Analysis**

**Official Title:** Zoledronic Acid for Osteoporotic Fracture Prevention (ZEST II)

**ClinicalTrials.gov ID (NCT number):** NCT02589600

**Document Date:** 3/30/2023

All statistical analyses will use SAS® version 9 (SAS Institute, Inc., Cary, North Carolina) based on intention-to-treat. First, appropriate descriptive statistics will be computed and graphical summarizations made for all variables for each treatment group for each time point as well as raw and percent change scores from baseline to obtain an overall sense of the distributional characteristics, missing values and general data quality. Second, baseline measures will be compared across arms using independent samples t- and a Wilcoxon rank sum tests, as appropriate, for continuous variables and chi-square and Fisher's exact tests, as appropriate, for categorical variables. Although no significant differences are expected due to randomization and large sample size, any variables found to be significantly different will be accounted for by including them as covariates in sensitivity analyses. Third, main analyses will be performed using a negative binomial regression model. Finally, exploratory analyses will be performed.

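### Does the primary fracture analysis need an explicit month-36 cut-off because fractures are also collected in the extension?

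*Protocol*

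**What the plan says.** In the Protocol, Statistical Considerations (Main Analyses), the H1 test comes from a negative binomial model "with each fracture outcome as the dependent variable; duration of follow-up as an offset to account for each" participant's exposure. No end point for that duration is given. The SAP adds only this: "Third, main analyses will be performed using a negative binomial regression model."

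Study Design & Methods describes a 3-year trial whose last main visit is month 36. It then adds a Follow-up Extension, requested by the DSMB, "to continue data collection on the skeletal health of participants in the ZEST II study." On treatment it says: "Therapy and blood work will not be provided throughout the follow-up extension." Entry depends on a calendar date: "Participants who do not complete the Month 36 visit before August 1, 2021 will not be eligible to participate in the follow-up extension." Women who enter have one, two or three visits according to when they completed month 36.

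Skeletal Assessments has clinical fractures identified from baseline until follow-up ends. It has vertebral fractures assessed at the annual trial visits and at extension visits 1 to 3. Eligibility Criteria adds: "Exclusion Criteria #3, #4, and #5 will not apply to participants in the Follow-up Extension phase of this study." Criterion 3 begins "Women currently on bisphosphonate, denosumab, or teriparatide therapy."

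Exploratory Analyses proposes stratifying adverse event and fracture "analyses to identify any differences between short- and long-term effects," without a time boundary and without naming the extension.

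**The concern.** The primary model's exposure term has no stated end, while the data-collection text runs past month 36. An analyst who took both literally could count extension fractures and extension person-time towards H1.

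That would matter because extension time is different. No study drug is given. Only women who complete month 36 by a fixed date contribute. The bar on entering while using another osteoporosis drug is lifted. Pooling would blend treated and later rates into one ratio, and a borderline H1 result could depend on the choice.

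The omission is not a matter of timing. Both documents are dated 30 March 2023, 607 days (about 20 months) after the last qualifying date for the extension, 31 July 2021. The extension fractures also have no stated analysis of their own.

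A smaller point concerns vertebral fractures seen only on the annual vertebral fracture assessment (VFA). If exposure for these runs to last contact, time after the last scan counts although no such fracture could be detected in it.

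**Working it through.** The documents give no sample size, event count or dropout rate, so there is no planned figure to reproduce. The first check is textual.

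| Place in the Protocol | Time frame |
|---|---|
| Primary Outcome | Women leaving before 3 years give partial person-months and fracture counts |
| Study Design & Methods | 3-year trial; month 36 is the last main visit |
| Main Analyses, laboratory models | 12-, 24- and 36-month time points |
| Main Analyses, adverse-event models | The 36-month follow-up |
| Aim 3(b), active-arm fracture model | Fractures over 3 years |
| Main Analyses, H1 model | Duration of follow-up, no end stated |
| Skeletal Assessments | Fracture collection continues into the extension |

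The first row decides the question. Person-months and fracture counts are the inputs to the H1 model, and someone who leaves before 3 years can be partial only if complete exposure is 3 years. The last row describes what is collected, not what is tested.

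The second check asks what pooling would do.

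*Inputs.* The 36-month rate ratio is 0.65, from the 35% reduction in clinical fractures cited in Study Design & Methods; it is not a design assumption of this trial. The following are assumed: annual loss L of 10-25%, one extension year per month-36 completer, an extension rate ratio of 0.85, equal control rates in both periods, and Poisson counts.

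*Person-time per woman.* With h = -ln(1-L), trial time is T = (1-(1-L)³)/h, and extension time is X = (1-L)³ × 1 year.
- L = 10%: T = 0.271/0.1054 = 2.572, X = 0.729, share X/(T+X) = 22%.
- L = 25%: T = 0.578/0.2877 = 2.010, X = 0.422, share = 17%.

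*Pooled rate ratio* = (0.65T + 0.85X)/(T+X).
- L = 10%: (1.672 + 0.620)/3.301 = 0.694.
- L = 25%: (1.307 + 0.359)/2.432 = 0.685.

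*Significance.* The Wald z is proportional to |ln(rate ratio)|/√(1/E₀ + 1/E₁), where E₀ and E₁ are the expected control and active counts. Scale it so that month 36 alone gives z = 1.96. At L = 10%, the month-36 term is 0.4308/0.9934 = 0.434 and the pooled term is 0.365/0.860 = 0.4245. So z = 1.96 × 0.4245/0.434 = 1.92 and p = 0.055. At L = 25%, p = 0.054.

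*Other assumptions, still one extension year.* If the effect persists in full (extension rate ratio 0.65), p = 0.026-0.031. If it vanishes from month 36 (1.0), the pooled ratio is 0.71-0.73 and p = 0.079-0.090.

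*Negative binomial check.* Assume 200 women per arm, dispersion 1, no loss, and 0.11 fractures a year (the nonvertebral incidence in Scientific Background). The variance of the log ratio is (1/n)(1/μ₀ + 1/μ₁ + 2). At 36 months μ₀ = 0.330 and μ₁ = 0.2145, giving 50% power. With one extension year per woman at a rate ratio of 0.80, μ₀ = 0.440 and μ₁ = 0.3025, giving 49%.

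*VFA point.* If exposure runs to last contact, the absolute VFA-only rate is understated by 1 - [(1-L) + (1-L)² + (1-L)³]/T. That is 1 - 2.439/2.572 = 5.2% at L = 10% and 1 - 1.734/2.010 = 13.7% at L = 25%. The factor cancels from the rate ratio if loss and scan attendance are equal by arm.

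**The case for a change.** The best case for a change is that a primary endpoint's window should be written down, not inferred. The authors state a window for adverse events and for Aim 3(b), yet not for the one model that carries the formal test. The collection text runs through the extension, and the plan was dated well after the extension was under way. One sentence would cost little and would remove any suspicion that the window was chosen after seeing results. All of that is true of the wording.

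The stakes are smaller than they first look. Total loss of effect from month 36 is the least supported scenario: the Protocol itself calls bisphosphonates long acting and reports improved density over 2 years after a single dose. These are not fracture data, but they count against an abrupt end of effect.

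A 2-year average extension would give larger shifts (30-36% of person-time) but is hard to reach. With yearly visits (assumed from the July dates) and 25% annual loss continuing, the most possible is 2.01 years, and only if every completer qualified for three visits. At 10% loss the ceiling is 2.57 years. An equal split across three, two, one and no visits gives 1.1-1.3 years.

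Waiving criterion 3 shows less than it seems to. It is an entry criterion, and the Protocol nowhere bars or censors other osteoporosis drugs started after randomisation. Such use is therefore not shown to be peculiar to the extension.

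**Conclusion.** The gap is real on the page: the H1 model prints no end of follow-up, and the extension is absent from all statistical text. It does not call for a change. The Primary Outcome paragraph fixes complete exposure at 3 years, the other stated windows agree, the extension is named and entered as a separate phase, and nothing proposes pooling it. An analyst working from these documents would close H1 counts and exposure at month 36 and treat later fractures as extension data, and the H1 result is then unaffected.

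If pooling did occur, the central illustration moves the rate ratio from 0.65 to about 0.69 and a borderline p from 0.050 to about 0.055. This rests on assumed loss, extension time and off-therapy effect, and on Poisson rather than negative binomial counts. Under other assumptions p can move either way.

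The missing boundary for short- and long-term effects belongs to exploratory work and can be set there. The VFA point concerns absolute rates only; with equal loss and attendance by arm it leaves the treatment comparison unbiased, so an added analysis would bring no gain.
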